10.1 Procedures by Visit

The Time and Events Schedule above (Table 1 - attached) summarizes the frequency and timing of various measurements. The evaluations and procedures for patients enrolled in this study at specific time points are further described in the following sections.

10.1.1 Screening/Pre-study (Day -28 to Day -1)

The following procedures will be completed for each patient prior to inclusion in the study. All screening diagnostic imaging studies MUST be performed within 28 days of the first treatment.

- Confirmation of the eligibility of patients (see Section 4 for detailed Inclusion/Exclusion criteria)
- Histologic diagnosis of HCC
- Demographics
- Medical history relevant to the patient's cancer
- Vital sign measurements including weight, height, temperature, pulse, oxygen saturation by pulse oximetry, and resting systolic and diastolic blood pressure
- Complete physical examination
- ECOG Performance Status
- Clinical laboratory tests
- Hematology: CBC
- Serum Chemistry Panel
- T3 (free), T4 (free) & TSH
- ACTH and Total Cortisol
- Amylase and Lipase
- Hepatitis B and C screening tests
- AFP (alpha fetoprotein)
- Serum IGF
- Blood samples for Immune Testing
- Urinalysis: Gross examination including specific gravity, protein, glucose, and blood; microscopic examination including WBC/HPF, RBC/HPF and any additional findings.
- A pregnancy test will be done for women of childbearing potential every 4 weeks during enrollment, beginning 24 prior to starting therapy, and prior to post-operative nivolumab treatment as explained in Section 4.1.
- Chest radiography
- Diagnostic imaging, including CT of the chest, abdomen and pelvis or MRI abdomen/pelvis.

- EKG
- Current medications
- Baseline signs and symptoms
- Tumor tissue Collection-
- Diagnostic/confirmatory biopsy

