AFP = alpha fetoprotein; aPTT = activated partial thromboplastin time; Anti-HBc (total) = Total hepatitis B core antibody; Anti-HDV = hepatitis D virus antibody (previously known as 'delta'); anti-HBs = hepatitis B surface antibody; BP = blood pressure; CBC = complete blood count; Discon = discontinuation; ECOG = Eastern Cooperative Oncology Group; FT4 = free thyroxine; HBeAb or anti-HBe = hepatitis B e antibody; HBeAg = hepatitis B e antigen; HBV = hepatitis B virus; HBcAg = hepatitis B core antigen; HBsAb = hepatitis B surface antibody; HBsAg = hepatitis B surface antigen; HCV = hepatitis C virus; HCV Ab = hepatitis C antibody; INR = international normalized ratio; P = pulse; Q12W = every 12 weeks; RR = respiratory rate; T = temperature; PT = prothrombin time; T3 = triiodothyronine; TSH = thyroid-stimulating hormone, ACTH = adrenocorticotropic hormone .

- a. In subjects that experience site-assessed PD or start a new anti-cancer therapy, contact should be made (example; by telephone) q12W to assess for survival status.
- b. Cycle 1 treatment must be given within 3 days of allocation. The window for each visit is ± 3 days until the end of treatment and ± 7 days during follow-up. Nivolumab is given every 4 weeks after surgery.
- c. Height will be measured at Visit 1 only.
- d. For women of reproductive potential, a urine or serum pregnancy test should be performed within 24 hours prior to C1D1, C5D1 and 30 days post treatment. May use screening pregnancy test if performed within 24 hours of first dose. A serum test can be done if urine is not appropriate. Additionally, if urine test is positive or is not evaluable, a serum test is required. Subjects must be excluded/discontinued in the event of a positive test results. Pregnancy tests (serum and/or urine tests) should be repeated if required by local guidelines.
- e. ECOG Performance Status and laboratory tests for screening and determining eligibility are to be performed within 28 days prior to the first dose of trial treatment.
- f. CBC with differential and chemistry to be performed every 2 weeks before surgery. After surgery, CBC with differential and chemistry are performed on every nivolumab administration day.
- g. Urinalysis and thyroid/hormonal function tests will be performed at every cycle before surgery, at time of surgery (C4D1), at C6D1 and at every restaging thereafter (q12 weeks).

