10.1.2 Pre-surgical Phase

Patients who complete the screening evaluations and are confirmed to be eligible for the study will begin treatment on this study.

Eligible patients in Arm A will receive nivolumab at 240 mg IV every 2 weeks for 3 doses (6 weeks) followed by hepatic resection.

Eligible patients in Arm B will receive nivolumab 240 mg IV every 2 weeks for 3 doses plus ipilimumab 1 mg/kg IV on day 1 of therapy (3 doses of nivolumab, 1 dose of ipilimumab; 6 weeks) followed by hepatic resection.

The following procedures will be performed within +/- 3 days of each scheduled visit or as indicated in Section 10.

- Vital sign measurements including weight, temperature, pulse, oxygen saturation by pulse oximetry, and resting systolic and diastolic blood pressure.
- Vital sign measurements of pulse, oxygen saturation by pulse oximetry, and systolic and diastolic blood pressure will be collected every 30 minutes for the duration of nivolumab +/- ipilimumab infusion, 1 hour following the completion of the infusion, and routinely unless otherwise indicated.
- Physical examination
- ECOG Performance Status
- Blood samples for Immune Tests
- Hematology: (see Section 10, PT and PTT will be done at baseline and prior to surgery or future procedures)
- Serum chemistry (see Section 10)
- Amylase & Lipase
- AFP
- T3 (free), T4 (free) & TSH (see Section 10)
- A pregnancy test will be done for women of childbearing potential on the day of starting therapy as explained in Section 4.1.
- Concomitant medications (see Section 9)

- Adverse event assessment
- Each patient will be restaged with CT of the chest, abdomen and pelvis or MRI abdomen/pelvis at baseline, prior to surgery, 8 weeks post-surgery follow up, and during future follow up visits (every 12 weeks) as indicated in Section 10, unless, in the investigators' opinion, follow-up intervals need to be shorter. Studies to confirm a complete response or document progressive disease will be performed as needed. Unscheduled visits are permitted to evaluate adverse events and possible disease progression.

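### Table 1 schedules no pregnancy test between C1D1 and C5D1 or during later adjuvant dosing, in conflict with the 4-weekly rule in Section 10.1.1

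*Combined protocol and SAP*

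**What the plan says.** Section 10.1.1 (Screening/Pre-study) has a bullet on pregnancy testing in women who could become pregnant, and sets the timing as "every 4 weeks during enrollment, beginning 24 prior to starting therapy, and prior to post-operative nivolumab treatment as explained in Section 4.1". The list that contains it opens with "The following procedures will be completed for each patient prior to inclusion in the study". The unit after 24 is missing.

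In Section 10.0, the Table 1 pregnancy-test row is marked in both arms at screening, C1D1, C5D1 and 30 days after the last dose. It is blank at C2D1, C3D1, C4D1 (surgery), C6D1, C7+D1 and discontinuation. Footnote d, identical in the two arms, says that "a urine or serum pregnancy test should be performed within 24 hours prior to C1D1, C5D1 and 30 days post treatment". It adds a stop rule, "Subjects must be excluded/discontinued in the event of a positive test results", and an open provision, "Pregnancy tests (serum and/or urine tests) should be repeated if required by local guidelines".

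Section 10.1 introduces the visit descriptions by saying "The Time and Events Schedule above (Table 1 - attached) summarizes the frequency and timing of various measurements". Among those descriptions, 10.1.2 (Pre-surgical Phase) says "A pregnancy test will be done for women of childbearing potential on the day of starting therapy"; the lists in 10.1.3 (Pre-surgical Visit) and 10.1.5 (Post-surgical Follow-Up) contain no pregnancy test. Section 4.1 requires one test in the 24 hours before study drug starts. Two further lines there make clear that testing goes on, but give no interval.

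**The concern.** The interval appears once, in a bullet placed under screening. The schedule that staff use visit by visit, and the footnote that spells it out, omit it. Two people following different parts of the same protocol would therefore test the same woman at very different frequencies.

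What is at stake is patient safety. Footnote d makes a positive test a reason to stop, and a stop rule works only if something looks for the condition. On the Table 1 schedule, two preoperative nivolumab doses (C2D1 and C3D1) and the hepatic resection pass with no scheduled test after C1D1. After C5D1, nothing is scheduled until dosing has ended. Detection in between would rest on the woman's or physician's suspicion, on local guidelines, or on discretionary laboratory work.

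**Working it through.** The plan states no figure to reproduce. The check is to read the two schedules against each other and count.

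**Nominal visit weeks**
- C1D1 = week 0, C2D1 = 2, C3D1 = 4 (nivolumab every 2 weeks, Section 5.3).
- C4D1, surgery on day 1 of week 7 (Section 5.3) = week 6.
- C5D1, 4 weeks after surgery (Section 5.3) = 6 + 4 = week 10. Table 1 footnote h places C6D1 at 8 weeks after surgery, which agrees.
- Later nivolumab every 4 weeks: weeks 14, 18, and so on.
- Treatment limit: 2 years (104 weeks) from first cycle, from the sentence in Section 5.3 that covers both arms.
- Arm B adjuvant ipilimumab: every 6 weeks from C5D1, at most 4 doses (footnote r), so weeks 10, 16, 22 and 28.

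**Gap before C5D1 on Table 1**
10 − 0 = 10 weeks with no scheduled test. With ±7 days at surgery and ±3 days at C5D1, the range is (70 − 10)/7 = 8.6 to (70 + 10)/7 = 11.4 weeks.

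**Gap after C5D1 on Table 1, for a woman who completes treatment**
- Last dose within 104 weeks: 10 + 4 × 23 = week 102, since the next would fall at week 106.
- Nivolumab doses after C5D1: (102 − 10)/4 = 23.
- Ipilimumab doses after C5D1 in Arm B: 4 − 1 = 3.
- Time to the next scheduled test, 30 days (4.3 weeks) after the last dose: 102 + 4.3 − 10 = 96.3 weeks.

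**What the 10.1.1 rule would require beyond Table 1**
Tests at about weeks 4 and 8, then one at each of the 23 later nivolumab visits: 2 + 23 = 25.

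**What the proposed schedule requires beyond Table 1**
Week 8 has no visit, so the second preoperative test goes to surgery at week 6. Tests at weeks 4 and 6 plus 23 later visits: 2 + 23 = 25. Successive intervals are 4, 2 and 4 weeks, then 4 throughout, so none exceeds 4 weeks nominally. For Arm B ipilimumab at weeks 10, 16, 22 and 28, the latest tests fall at weeks 10, 14, 22 and 26, that is 0, 2, 0 and 2 weeks earlier.

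**The case against.** The strongest reply is that the safeguard is already in the protocol. The 10.1.1 bullet is an instruction, and Section 10.1 describes Table 1 as a summary whose procedures are described further in the sections that follow. A screening-only reading does not survive the bullet's own terms. A 4-weekly series that starts 24 hours before dosing (hours being the evident unit, from Section 4.1 and footnote d) can repeat only on treatment, and the bullet names post-operative nivolumab. Section 4.1 likewise says that testing continues.

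This stands. A reader might infer from Table 1 that the protocol leaves pregnancy unmonitored for up to two years. The documents do not support that: the gaps arise only for a team working from Table 1 and footnote d. A reader might also infer a gap with no upper limit from Section 6.1.3, which states no time cap for adjuvant nivolumab. But Section 5.3 limits treatment to 2 years, and the Table 1 headers in both arms say the same.

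It is also fair to say that Table 1 is not the only route to a test. Footnote d allows repeats under local guidelines, Section 10.1.4 allows additional safety laboratory tests at the surgeon's discretion, and Section 11.4 requires immediate notification of a suspected pregnancy. None of these is a scheduled test.

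What the reply does not remove is the conflict itself. Footnote d is explicit about when tests fall and gives no pointer to a 4-weekly rule, and the visit lists after 10.1.1 do not carry the rule forward.

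**Conclusion.** The concern holds as an internal inconsistency: Section 10.1.1 sets a 4-weekly interval, and Table 1 with footnote d sets a much sparser schedule for the same test in both arms. For a team that follows Table 1, the consequence is 10 weeks without a scheduled test before C5D1 and about 96 weeks after it.

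Those figures assume nominal visit timing, and the second also assumes a woman who completes 2 years from first cycle. It is shorter if dosing stops early.

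The point is minor. It touches no endpoint, sample size or analysis. The documents do not give the number of women of childbearing potential, and because enrollment has stopped, the benefit is limited to those still on treatment. It is worth correcting because it concerns a mandatory stop condition and the correction is cheap.

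**What to change.** Bring Table 1 into line with the protocol's own 4-weekly rule, in both arms:

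- Mark the pregnancy-test row at C3D1, C4D1 (before the operation), C6D1 and C7+D1.
- Amend the timing sentence of footnote d to require a urine or serum test within 24 hours before C1D1, at C3D1, preoperatively at C4D1, within 24 hours before C5D1 and each later 4-weekly nivolumab dose, and 30 days after treatment. Leave the stop rule and the local-guideline provision as they are.
- In 10.1.1, supply the missing word so that it reads 24 hours, and state that the rule applies throughout treatment.
- Add the test to the 10.1.5 list.

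The cost is a protocol amendment and about 25 extra urine or serum tests per woman of childbearing potential who completes 2 years from first cycle, counted against Table 1. Counted against 10.1.1, the extra is roughly none. No extra visits are needed while dosing is on schedule. Table 1 already marks blood counts and chemistry at C3D1 and C4D1, and footnote f for Arm A says "After surgery, CBC with differential and chemistry are performed on every nivolumab administration day"; the Arm B footnote extends this to ipilimumab days.

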10.1.2 Pre-surgical Phase

Patients who complete the screening evaluations and are confirmed to be eligible for the study will begin treatment on this study.

Eligible patients in Arm A will receive nivolumab at 240 mg IV every 2 weeks for 3 doses (6 weeks) followed by hepatic resection.

Eligible patients in Arm B will receive nivolumab 240 mg IV every 2 weeks for 3 doses plus ipilimumab 1 mg/kg IV on day 1 of therapy (3 doses of nivolumab, 1 dose of ipilimumab; 6 weeks) followed by hepatic resection.

The following procedures will be performed within +/- 3 days of each scheduled visit or as indicated in Section 10.

- Vital sign measurements including weight, temperature, pulse, oxygen saturation by pulse oximetry, and resting systolic and diastolic blood pressure.
- Vital sign measurements of pulse, oxygen saturation by pulse oximetry, and systolic and diastolic blood pressure will be collected every 30 minutes for the duration of nivolumab +/- ipilimumab infusion, 1 hour following the completion of the infusion, and routinely unless otherwise indicated.
- Physical examination
- ECOG Performance Status
- Blood samples for Immune Tests
- Hematology: (see Section 10, PT and PTT will be done at baseline and prior to surgery or future procedures)
- Serum chemistry (see Section 10)
- Amylase & Lipase
- AFP
- T3 (free), T4 (free) & TSH (see Section 10)
- A pregnancy test will be done for women of childbearing potential on the day of starting therapy as explained in Section 4.1.
- Concomitant medications (see Section 9)

- Adverse event assessment
- Each patient will be restaged with CT of the chest, abdomen and pelvis or MRI abdomen/pelvis at baseline, prior to surgery, 8 weeks post-surgery follow up, and during future follow up visits (every 12 weeks) as indicated in Section 10, unless, in the investigators' opinion, follow-up intervals need to be shorter. Studies to confirm a complete response or document progressive disease will be performed as needed. Unscheduled visits are permitted to evaluate adverse events and possible disease progression.

10.1.3 Pre-surgical Visit

During the Pre-Surgical Evaluation, the patient will have labs and imaging performed and be assessed by the physician and surgeon to determine if they are still good candidates for surgery. For the pre-surgical visit, patients will return to the clinic at week 6 (+/- 7 days). The following assessments will be conducted during this visit:

- Vital Signs Measurement
- Physical examination
- ECOG Performance Status
- Blood samples for Immune Tests
- Hematology, PT and PTT
- Serum chemistry (see Section 10)
- Amylase and Lipase
- AFP
- T3 (free), T4 (free) & TSH (see Section 10)
- ACTH and Total Cortisol
- Concomitant medications (see Section 9)
- Adverse event assessment
- Each patient will be restaged with CT of the chest, abdomen and pelvis or MRI abdomen/pelvis at baseline, prior to surgery, 8 weeks post-surgery follow up, and during future follow up visits (every 12 weeks) as indicated in Section 10, unless, in the investigators' opinion, follow-up intervals need to be shorter. Studies to confirm a complete response or document progressive disease will be performed as needed.

10.1.4 Surgery Visit

During the Surgical Visit the patient will have a hepatic resection or biopsy performed by the surgeon and tissue will be collected. For the surgical visit, patients will return to the clinic at week 7 (+/- 7 days). The following assessments will be conducted during this visit:

- Surgery or biopsy

- Tumor tissue collection for immune tests
- Additional safety lab tests at the surgeon's discretion
- Tumor tissue collection for immunological testing (at surgery).
- As an optional procedure, tissue will also be collected during procedures performed while patients are enrolled in this study. No new procedures will be required. This tissue will also be banked for future research related to immunological response.

10.1.5 Post-surgical Follow-Up (4 Weeks Post Surgery) & Post-Op Nivolumab or Nivolumab/Ipilimumab Maintenance

The Post-Surgical Follow Up begins for all patients after surgery. Patients will return to the clinic for a follow-up visit 4 weeks postsurgery. The following assessments will be conducted during this visit:

- Vital Signs Measurement
- Physical examination
- ECOG Performance Status
- Blood samples for Immune Tests
- Hematology
- Serum chemistry (see Section 10)
- Amylase and Lipase
- AFP
- T3 (free), T4 (free) & TSH (see Section 10)
- Concomitant medications (see Section 9)
- Adverse event assessment
- Each patient will be restaged with CT of the chest, abdomen and pelvis or MRI abdomen/pelvis at baseline, prior to surgery, 8 weeks post-surgery follow up, and during future follow up visits (every 12 weeks) as indicated in Section 10, unless, in the investigators' opinion, follow-up intervals need to be shorter. Studies to confirm a complete response or document progressive disease will be performed as needed.

Patients will be followed for clinical responses, anti-cancer medications and delayed autoimmune toxicity and TTP. If a possible delayed Immune-related adverse event (IRAE) is suspected, the patient will be requested to return to the Investigator's clinic or office for a physical examination and blood work, and other relevant laboratory assessments. All patients will be followed for immune-related adverse events for at least 30 days after finishing therapy.

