After finishing the last treatment, hepatic resection or biopsy will occur on day 1 of week 7 (+/- 7 days). We will obtain surveillance scans (MRI of abdomen and pelvis with/without contrast, and CT chest with/without contrast of chest) 8 weeks after surgery. Patients who show significant progression of disease post-operatively will be taken off study and an optional biopsy will be taken at that time for immunological analysis.

Patients who complete the study or discontinue study treatment should be scheduled for an end of treatment visit (EOT) as soon as possible. All patients who complete the study or discontinue treatment will have a safety follow-up visit 30 (+/- 14 days) after the last dose of study drug or surgery, whichever comes last. Please refer to **Figure 2** below for the study design.

Patients will receive baseline staging studies with CT or MRI and be assessed for treatment response by scans: MRI or CT of abdomen and pelvis with/without contrast, and CT chest with/without contrast of chest (according to RECIST 1.1 and irRC) at week 6 (+/- 7 days). Each patient will have post-surgical (day 1 of week 11 +/- 7 days), staging studies as above. Subsequently, restaging will be carried out every 12 weeks unless, in the investigators' opinion, follow-up intervals need to be shorter. Studies to confirm a complete response or document progressive disease will be performed as needed. Patients will be allowed to continue study therapy after initial investigator-assessed RECIST 1.1/irRC-defined progression if they are deemed by the investigator to be deriving clinical benefit and tolerating study drug(s), as described in Section 8.3.

[figure not shown]

Figure 2. Study Design of preoperative nivolumab alone or in combination with ipilimumab. There are 2 arms to this study: A) Nivolumab monotherapy in resectable HCC; B) Combination nivolumab plus ipilimumab in resectable HCC.

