10.0 STUDY ASSESSMENTS AND PROCEDURES

Table 1: Study Assessments and Procedures for Arm A

Trial Period:	Screening Phase	Treatment Cycles. 3 cycles (2-Week Cycles) planned before surgery then after surgery (4-Week Cycles), patients may receive up to 2 years of therapy depending on response and every restaging scans every 12 weeks							End of Treatment	Post-treatment		
					Surgery					Discontinue	Safety Follow-up ¹	Follow-Up Visits
Title:	Screening											
Treatment Cycle/Day:	0	C1D1	C2D1	C3D1	C4D1	C5D1	C6D1	C7+D1	At time of discon	30 days post last dose	Every 9 weeks post-discon	Every 12 weeks
Scheduling Window (Days) ^b	-28 to -1	±3	±3	±3	±7	±3	±3	±3	±3	±7	±7	±7
Administrative Procedures												
Informed consent	X											
Informed consent for future biomedical research (optional)	X											
Inclusion/exclusion criteria	X											

Trial Period:	Screening Phase	Treatment Cycles. 3 cycles (2-Week Cycles) planned before surgery then after surgery (4-Week Cycles), patients may receive up to 2 years of therapy depending on response and every restaging scans every 12 weeks							End of Treatment	Post-treatment		
Title:	Screening				Surgery				Discontinue	Safety Follow-up¹	Follow-Up Visits	Survival Follow-Up^a
Treatment Cycle/Day:	0	C1D1	C2D1	C3D1	C4D1	C5D1	C6D1	C7+D1	At time of discon	30 days post last dose	Every 9 weeks post-discon	Every 12 weeks
Scheduling Window (Days)^b	-28 to -1	±3	±3	±3	±7	±3	±3	±3	±3	±7	±7	±7
Demographics and medical history	X											
Prior and concomitant medication review	X	X	X	X	X	X	X	X	X	X		
Post-study anticancer therapy status										X	X	X
Survival status												X
Clinical Procedures/Assessments												
Review adverse events	X	X	X	X	X	X	X	X	X	X	X	
Full physical examination	X								X	X		
Directed physical examination ^c		X	X	X	X	X	X	X				
Child-Pugh score	X											
Height, weight, and vital signs (T, P, RR, BP) ^c	X	X	X	X	X	X	X	X	X			
12-Lead electrocardiogram	X											
Upper endoscopy ^p	X											
ECOG performance status	X ^e	X	X	X	X	X	X	X	X			
Nivolumab administration		X ^b	X	X		X ^b	X	X				
LOCAL Laboratory Assessments												
Pregnancy test ^d	X	X				X				X		
PT/INR and PTT	X ^e	X	X	X	X	X	X	X	X	X		
CBC with differential ^f	X ^e	X	X	X	X	X	X	X	X	X		

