Trial Period:	Screening Phase	Treatment Cycles. 3 cycles (2-Week Cycles) planned before surgery then after surgery (4-Week Cycles), patients may receive up to 2 years of therapy depending on response and every restaging scans every 12 weeks							End of Treatment	Post-treatment		
Title:	Screening				Surgery				Discontinue	Safety Follow-up¹	Follow-Up Visits	Survival Follow-Up^a
Treatment Cycle/Day:	0	C1D1	C2D1	C3D1	C4D1	C5D1	C6D1	C7+D1	At time of discon	30 days post last dose	Every 9 weeks post-discon	Every 12 weeks
Scheduling Window (Days)^b	-28 to -1	±3	±3	±3	±7	±3	±3	±3	±3	±7	±7	±7
Chemistry panel ^f	X ^e	X	X	X	X	X	X	X	X	X		
Urinalysis ^g	X ^e	X	X	X	X		X ^q		X			
T3, FT4, TSH, ACTH, and total cortisol ^g	X ^e	X	X	X	X		X ^q		X	X		
AFP ^p	X ^e	X			X		X ^q		X	X		
C -Reactive protein, amylase, lipase		X			X		X ^q		X			
Serum IGF	X ^q	X			X		X ^q		X			
Hepatitis C antibody (HCV Ab, anti-HCV)	X											
Anti-HBc (Total and IgM), anti-HBs, HBsAg	X											
If Anti-HCV (Hepatitis C antibody) positive:												
• HCV genotype	X											
• HCV viral load ⁿ	X	X			X		X ^q		X			
If (1) HBsAg positive or (2) anti-HBc positive, anti-HBs negative, and HBsAg negative:												
• Anti-HDV	X											
• Anti-HBe and HBeAg	X											

Trial Period:	Screening Phase	Treatment Cycles. 3 cycles (2-Week Cycles) planned before surgery then after surgery (4-Week Cycles), patients may receive up to 2 years of therapy depending on response and every restaging scans every 12 weeks							End of Treatment	Post-treatment		
					Surgery					Discontinue	Safety Follow-up ^l	Follow-Up Visits
Title:	Screening											
Treatment Cycle/Day:	0	C1D1	C2D1	C3D1	C4D1	C5D1	C6D1	C7+D1	At time of discon	30 days post last dose	Every 9 weeks post-discon	Every 12 weeks
Scheduling Window (Days) ^b	-28 to -1	±3	±3	±3	±7	±3	±3	±3	±3	±7	±7	±7
• HBV viral load ⁿ	X				X		X ^q		X			
• Anti-HBc (total), anti-HBs, and HBe Ag	X											
CENTRAL Laboratory Assessments												
Blood for genetic analysis		X										
Whole blood for biomarker studies (serum and plasma) ^h		X	X	X	X		X ^q		X			
Whole blood for correlative studies (RNA and DNA) ^h		X	X	X	X		X ^q		X			
Tumor tissue collection ^j	X				X							
Efficacy Measurements												
Tumor imaging ^k	X ^{i, n}				X		X ^q		X			

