- h. Blood will be collected prior to dose one (C1D1), Cycle 2 and 3 (before the 2nd and 3rd dose of Nivolumab), at time of surgery (C4D1), at 8 weeks after surgery (C6D1), at every restaging thereafter (q12 weeks), and finally at treatment discontinuation (confirmed progression or end of therapy).
- i. Screening tumor imaging will be performed within 28 days prior to allocation for confirmation of baseline measurable disease per RECIST 1.1 as required prior to subject allocation, then at time of surgery. After surgery, imaging will be repeated and therapy starts at C7D1, then surveillance imaging will be repeated q12W (72 \pm 7 days).
- j. Biopsies will be required pre-treatment and at time of surgery.
- k. The first on-study imaging time point will be performed at 6 weeks around time of surgery (42 \pm 7 days) calculated from the date of allocation and then 8 weeks after surgery, and will continue to be performed q12W.
- l. SAEs will be followed through 100 days following cessation of treatment, or 100 days following cessation of treatment if the subject initiates new anticancer therapy, whichever is earlier.
- m. HBV/HCV viral loads (for subjects who have known history of chronic infection) will be measured during screening, then at C1D1, at time of surgery (C4D1), at 8 weeks after surgery (C6D1), at every restaging thereafter (q12 weeks), and at time of discontinuation.
- n. The following imaging studies are required at screening, at time of surgery, at 8 weeks after surgery, then at every restaging thereafter (q12 weeks): CT chest with or without contrast; MRI of abdomen and pelvis with or without contrast unless patient has contraindication for MRI or severely claustrophobic.
- o. Every time imaging is done for re-staging (q12 weeks).

Trial Period:	Screening Phase	Treatment Cycles. 3 cycles (2-Week Cycles) planned before surgery then after surgery (4-Week Cycles), patients may receive up to 2 years of therapy depending on response and every restaging scans every 12 weeks							End of Treatment	Post-treatment		
Title:	Screening				Surgery				Discontinue	Safety Follow-up ^l	Follow-Up Visits	Survival Follow-Up ^a
Treatment Cycle/Day:	0	C1D1	C2D1	C3D1	C4D1	C5D1	C6D1	C7+D1	At time of discon	30 days post last dose	Every 9 weeks post-discon	Every 12 weeks
Scheduling Window (Days) ^b	-28 to -1	±3	±3	±3	±7	±3	±3	±3	±3	±7	±7	±7

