12.2.2 Secondary Endpoints

12.2.2.1. *Objective Response Rate (ORR)*

Objective response rate (ORR) is defined as the number of subjects with a best response of CR or PR after 12 weeks of therapy by RECIST 1.1 criteria divided by the number of randomized subjects as described in Section 10.3.4.2

12.2.2.2. *Time to progression (TTP)*

TTP is defined as the time from the start of study drug to the first documented tumor progression or recurrence of tumor as determined by the investigator using RECIST 1.1 or iRC criteria. Patients who are alive and free of known progression at the time of analysis will be censored on the date of last tumor assessment.

12.2.2.3 *PFS*

PFS is defined as the time from the start of treatment to date of PD or recurrence or date of death whichever occurs first if patients have a event, or to the last follow-up date if patients are alive without PD.

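### Table 1 marks no tumor imaging after treatment discontinuation while its footnotes and the text continue 12-weekly scans without a stated end, so TTP and PFS follow-up is undefined for patients who stop without progression

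*Combined protocol and SAP*

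**What the plan says.** **Text.** Section 5.3, after the post-surgical scan: "Subsequently, restaging will be carried out every 12 weeks". Sections 10.1.2, 10.1.3 and 10.1.5 each restage patients "during future follow up visits (every 12 weeks) as indicated in Section 10". Section 10.1.5 adds: "Patients will be followed for clinical responses, anti-cancer medications and delayed autoimmune toxicity and TTP". None of these limits scanning to the treatment period or says when it ends.

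**Table 1 grid (Section 10.0, Arms A and B).** The row "Tumor imaging ^k" is marked at screening, C4D1 (surgery), C6D1 (with footnote q) and discontinuation. It is blank at the 30-day safety visit, at the follow-up visits ("Every 9 weeks post-discon") and at survival follow-up.

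**Table 1 footnotes.** Footnote k, attached to that row, places a scan around surgery "and then 8 weeks after surgery, and will continue to be performed q12W". Footnotes i and n likewise carry imaging forward every 12 weeks. Footnote q starts the 12-weekly assessments at Cycle 6, and the 12-weekly restaging also appears in the header over the treatment cycles. Footnote a: "In subjects that experience site-assessed PD or start a new anti-cancer therapy, contact should be made" every 12 weeks for survival status.

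**Withdrawal.** Section 8.0 lists reasons for which patients must both stop therapy and leave the study. One is an adverse event that, in the investigator's opinion, makes further treatment not in the patient's best interest.

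**Censoring.** For TTP (12.2.2.2): "Patients who are alive and free of known progression at the time of analysis will be censored on the date of last tumor assessment". For PFS (12.2.2.3), patients alive without progression are followed to the last follow-up date, whether or not a scan was done then.

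**The concern.** TTP and PFS need tumor assessment to continue until progression, including in patients who have stopped treatment. Footnote a moves patients with progression or new therapy to survival contact, so by implication the 9-weekly follow-up visits serve mainly patients who stopped without progression. These are the patients still at risk for the endpoint. At those visits the grid marks only adverse event review and post-study anticancer therapy status.

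Sites commonly schedule from the grid. A coordinator doing so here would stop scanning such a patient after the discontinuation scan, whereas one working from the text or footnotes would continue. The resulting TTP and PFS data would then depend on which part of the protocol was used. Section 12.6 uses Kaplan-Meier PFS per arm and names TTP among the results that will guide development.

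**Working it through.** No sample size, power or event count in the plan depends on this point, so there is no stated figure to reproduce. The check is a comparison of the passages, followed by an illustration of size.

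**Step 1. Read the grid by column.** Each row has a label and 12 visit columns. The adverse event row (marked through the follow-up visits) and the anticancer therapy row (marked in all three post-treatment columns) confirm the alignment. Post-treatment imaging marks: Arm A 0 of 3; Arm B 0 of 3.

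**Step 2. Set the sources side by side for a patient who stops without progression.**

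| Source | Scan after discontinuation? | Interval |
|---|---|---|
| Table 1 grid | Not marked | Visits every 9 weeks |
| Footnote q and treatment-cycle header | Series tied to treatment cycles | 12 weeks |
| Footnotes i, k, n | Continues, no end stated | 12 weeks |
| Section 5.3 | Continues, no end stated | 12 weeks |
| Sections 10.1.2, 10.1.3, 10.1.5 | At future follow-up visits, no end stated | 12 weeks |
| Section 8.1 | Addresses dosing interruption only | As per protocol |
| Section 8.0 | Some adverse event stops are withdrawn from the study | None |

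No passage settles which governs. The 9-week visits (63 days) and 12-week scans (84 days) do not coincide visit by visit.

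**Step 3. Follow the endpoint rules if the grid is used.**
- TTP: the last tumor assessment is the discontinuation scan, so the patient is censored there. Later information is lost. The Kaplan-Meier estimate within an arm is biased only if stopping is related to recurrence risk in that arm.
- PFS: censoring is at last follow-up. Each later visit without a scan adds time counted as progression-free, although progression was not looked for. Undetected recurrences stay in the risk set as event-free, which pushes the curve upward.

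**Step 4. Illustrate the size.** Section 3.2 of the protocol cites five-year recurrence after resection as high as 70%. The lower value of 50% at five years is an assumption, as is the constant hazard.

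Monthly hazard h = −ln(1 − R)/60:
- R = 0.50: h = 0.693/60 = 0.01155
- R = 0.70: h = 1.204/60 = 0.02007

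Probability of recurrence over m unscanned months = 1 − exp(−h·m). Scans omitted ≈ m × 30.4375/84.

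| Unscanned months | R = 50% | R = 70% | 12-weekly scans omitted |
|---|---|---|---|
| 6 | 6.7% | 11.3% | about 2 |
| 12 | 12.9% | 21.4% | about 4 |
| 18 | 18.8% | 30.3% | about 6 |

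These are chances for one patient who stops recurrence-free. Turning them into a number of missed recurrences needs the number of patients who stop without progression, which the documents do not give.

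**The case against.** The strongest answer is that footnotes belong to the table. Footnote k sits on the imaging row itself, and footnotes i and n agree with it, so Section 10 does provide for continued 12-weekly imaging. Section 5.3 says the same without limiting it to treatment. The text also allows studies as needed to document progression, and unscheduled visits for suspected progression. This stands against two readings that a reader might infer: that Table 1 provides for no imaging after discontinuation, and that recurrence then goes unmeasured. The documents support only that the grid marks none and that other passages disagree.

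The 9- and 12-week figures may describe different things, a visit interval and a scan interval. That is possible. However, Sections 10.1.2, 10.1.3 and 10.1.5 tie the 12-week figure to follow-up visits, so the mismatch still needs resolving.

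A reader might also infer that Arm B is demonstrably biased relative to Arm A, because the cited melanoma phase 3 study reports grade 3-4 related events of 55% against 16.3%. The documents do not support that:
- That study used ipilimumab 3 mg/kg every 3 weeks. The lung cancer cohorts cited with 1 mg/kg report 33% to 37%.
- Such events are not the same as discontinuations.
- Different amounts of censoring between arms do not by themselves bias a within-arm Kaplan-Meier curve.
- No between-arm test of TTP or PFS is planned.

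An effect that differs by arm is plausible in direction only.

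Finally, for patients withdrawn under Section 8.0, scanning would end whatever the grid shows. That is correct, and it means that marking the grid alone would not resolve the conflict.

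**Conclusion.** The concern holds as an unresolved internal conflict: the plan does not determine whether patients who stop without progression continue to be scanned. The grid, footnote q and the treatment-cycle header point one way; footnotes i, k and n and Sections 5.3 and 10.1 point the other; Section 8.0 removes some patients entirely.

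The harm is conditional on a site following the grid. In that case TTP follow-up is cut at the discontinuation scan and PFS can be biased upward by its censoring rule. The size is about 13% to 21% recurrence per unscanned year for each affected patient, under the constant hazard and the 50% to 70% range. The number affected and any difference by arm cannot be derived from the documents.

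The consequence is limited. TTP and PFS are secondary and descriptive in a pilot of up to 30 patients, of whom 27 were randomized, and the primary safety endpoint is unaffected. A correction should be made because these estimates are meant to inform later trials.

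**What to change.** 1. In both Table 1 grids, mark tumor imaging in the Follow-Up Visits column for patients who discontinue without progression, until progression, new anticancer therapy, consent withdrawal or study end. Say the same in footnotes i, k, n and q and in Sections 5.3 and 10.1.2 to 10.1.5. Keep footnote a for patients who have progressed or started new therapy.
2. Reconcile the 9-week visit interval with the 12-week restaging interval, or state how the two run together.
3. Reconcile Section 8.0 with the follow-up schedule, for example by stating that stopping treatment for an adverse event does not by itself end tumor follow-up.
4. In 12.2.2.3, censor PFS at the last tumor assessment, as 12.2.2.2 already does for TTP.

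The cost is a short amendment and a few off-treatment scans that the text already promises. Where patients have already stopped without later scans, item 4 still limits the upward bias in PFS.
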